8.3.1. Time Period and Frequency for Collecting AE and SAE Information

All AEs and SAEs will be collected from the time of signing of the informed consent form (ICF) until participation in the study has ended.

Adverse events that begin before the start of study intervention but after signing of the ICF will be recorded on the Adverse Event CRF.

Although all AEs after signing the ICF are recorded by the site in the CRF/electronic data entry, SAE reporting to sponsor begins after the participant has signed the ICF and has received study intervention. However, if an SAE occurs after signing the ICF, but prior to receiving study intervention, it needs to be reported within the SAE reporting timeframe if it is considered reasonably possibly related to study procedures.

All SAEs will be recorded and reported to the sponsor or designee immediately and under no circumstance should this exceed 24 hours, as indicated in Section 10.3, Appendix 3. The investigator will submit any updated SAE data to the sponsor within 24 hours of it being available.

Investigators are not obligated to actively seek AEs or SAEs after conclusion of the study participation. However, if the investigator learns of any SAE, including a death, at any time after a participant has been discharged from the study, and he/she considers the event to be reasonably related to the study intervention or study participation, the investigator must promptly notify the sponsor.

8.3.2. Method of Detecting AEs and SAEs

The method of recording, evaluating, and assessing causality of AE and SAE and the procedures for completing and transmitting SAE reports are provided in Section 10.3.

Care will be taken not to introduce bias when detecting AEs and/or SAEs. Open-ended and non-leading verbal questioning of the participant is the preferred method to inquire about AE occurrences.

8.3.3. Follow-up of AEs and SAEs

After the initial AE/SAE report, the investigator is required to proactively follow each participant at subsequent visits/contacts. All SAEs will be followed until resolution, stabilization, the event is otherwise explained, or the participant is lost to follow-up (as defined in Section 7.3). Further information on follow-up procedures is provided in Section 10.3.

8.3.4. Regulatory Reporting Requirements for SAEs

Prompt notification by the investigator to the sponsor of a SAE is essential so that legal obligations and ethical responsibilities towards the safety of participants and the safety of a study intervention under clinical investigation are met.

The sponsor has a legal responsibility to notify both the local regulatory authority and other regulatory agencies about the safety of a study intervention under clinical investigation. The sponsor will comply with country-specific regulatory requirements relating to safety reporting to the regulatory authority, Institutional Review Boards (IRB)/Independent Ethics Committees (IEC), and investigators.

An investigator who receives an investigator safety report describing a SAE or other specific safety information (e.g., summary or listing of SAEs) from the sponsor will review and then file it with the Investigator's Brochure, and will notify the IRB/IEC, if appropriate according to local requirements.

8.3.5. Pregnancy

Although normal pregnancy is not an adverse event, details of all pregnancies in female participants will be collected for 90 days after dosing.

If a pregnancy is reported, the investigator should inform the sponsor within 24 hours of learning of the pregnancy and should follow the procedures outlined in Section 10.4, Appendix 4.

Abnormal pregnancy outcomes, for example, spontaneous abortion, fetal death, stillbirth, congenital anomalies, and ectopic pregnancy, are considered SAEs.

8.3.6. Hypersensitivity Reactions

Many drugs, but particularly biologic agents, carry the risk of systemic hypersensitivity reactions.

If such a reaction occurs, additional details describing each symptom should be provided to the sponsor in the infusion-related reaction/hypersensitivity CRF.

If symptoms and/or signs occur during or within 6 hours after infusion of LY3819253 and are believed to be hypersensitivity or due to cytokine release, then investigators are encouraged to report the event as infusion-related immediate hypersensitivity reaction or cytokine release-associated infusion reaction, respectively.

Sites should have appropriately trained medical staff and appropriate medical equipment available when study participants are receiving intervention. It is recommended that participants who experience a systemic hypersensitivity reaction be treated per the local standard of care.

In the case of generalized urticaria or anaphylaxis, additional blood and urine samples should be collected as described in Section 10.6, Appendix 6, "Recommended Laboratory Testing for Hypersensitivity Events". Laboratory results are provided to the sponsor via the central laboratory.

In case of skin lesions or rash consistent with vasculitis, efforts should be made to perform the following as soon as possible

- dermatology consultation
- skin biopsy, and
- photographs of lesions of interest, including skin biopsy site.

8.3.7. Infusion-related Reactions

As with other mAbs, infusion-related reactions may occur during or following LY3819253 administration. If an infusion-related reaction occurs, additional data describing each symptom and sign should be provided to the sponsor in the CRF.

This table describes the location of infusion-related reaction information in t	this protocol.
---	----------------

Торіс	Location
Special treatment considerations	Section 6.1.1
Premedication for infusions	Section 6.1.1.1
Management of infusion reactions	Section 6.1.1.2
DAIDS table describing severity	Section 6.1.1.2

Symptoms occurring during or after infusion of study intervention may also be defined according to AE categories such as acute allergic reaction or cytokine release syndrome (refer to DAIDS).

8.3.8. Product Complaints

A product complaint is any written, electronic, or oral communication that alleges deficiencies related to the identity, quality, durability, reliability, safety, effectiveness or performance of a trial intervention.

The sponsor collects product complaints on study interventions used in clinical studies in order to ensure the safety of study participants, monitor quality, and to facilitate process and product improvements.

Participants will be instructed to contact the investigator as soon as possible if they have a complaint or problem with the study intervention so that the situation can be assessed.

NOTE: Any AEs or SAEs that are associated with a product complaint will follow the processes outlined in Section 8.3.3 and Appendix 10.3 of the protocol.

Time Period for Detecting Product Complaints

Product complaints that result in an adverse event will be detected, documented, and reported to the sponsor during all periods of the study in which the study intervention is used.

If the investigator learns of any product complaint at any time after a participant has been discharged from the study, and such incident is considered reasonably related to the study intervention, the investigator will promptly notify the sponsor.

Prompt Reporting of Product Complaints to Sponsor

Product complaints will be reported to the sponsor within 24 hours after the investigator becomes aware of the complaint.

The Product Complaint Form will be sent to the sponsor by a method designated by the sponsor.

Follow-up of Product Complaints

Follow-up applies to all participants, including those who discontinue study intervention.

The investigator is responsible for ensuring that follow-up includes any supplemental investigations as indicated to elucidate the nature and/or causality of the product complaint.

New or updated information will be recorded on the originally completed form with all changes signed and dated by the investigator and submitted to the sponsor.

8.4. Treatment of Overdose

In case of suspected overdose, participants should be monitored for any signs or symptoms of adverse reactions or effects, and supportive care should be provided as necessary.

8.5. Pharmacokinetics

Venous blood samples will be collected as specified in the SoA for determination of concentrations of LY3819253 used to evaluate the PK for LY3819253.

A maximum of 3 samples may be collected at additional time points during the study if warranted and agreed upon between the investigator and the sponsor.

Instructions for the collection and handling of biological samples will be provided by Lilly.

Site personnel will record

- The date and time (24-hour clock time) of administration (start and end of infusion), and
- The date and time (24-hour clock time) of each PK sample.

It is essential that the times are recorded accurately.

8.5.1. Bioanalytical

Samples will be analyzed at a laboratory approved by the sponsor and stored at a facility designated by the sponsor. Concentrations of LY3819253 will be assayed using a validated bioanalytical method. Analyses of samples collected from placebo-treated subjects are not planned.

Sample retention is described in Appendix 1, Section 10.1.12. Remaining samples used for PK may be pooled and used for exploratory metabolism or bioanalytical method experiments as deemed appropriate.

8.6. Pharmacodynamics

The SARS-CoV-2 viral RNA level and viral clearance will be evaluated by either a nasopharyngeal swab or mid-turbinate swab at times specified in the SoA. The same method of sample collection must be used per participant for the duration of the study. Switching methods for a participant is not allowed.

The nasopharyngeal swab is the preferred method and will be taken from both nostrils. The nasopharyngeal procedure is described in Section 10.7.

Sample retention is described in Section 10.1.12. Remaining samples may be used for additional exploratory studies to better understand LY3819253 and the disease, which may include sequencing and/or culture of the virus for future studies.

8.7. Genetics

A whole blood sample will be collected for pharmacogenetic analysis where local regulations allow.

See Section 10.2 Clinical Laboratory Tests, and Section 1.3 SoA for sample collection information.

See Section 10.5 for genetic research, custody, and sample retention information.

8.8. Biomarkers

Blood samples will be collected from all participants for analysis of immune system-related markers. Serum, whole blood for cellular and/or epigenetic analysis, and whole blood RNA samples for exploratory biomarker research will be collected at the time specified in the SoA where local regulations allow.

Samples will be stored and analysis may be performed on biomarkers thought to play a role in immune system related responses to viral infection including, but not limited to, immune pathways, cellular composition, serum analytes, or epigenetic biomarkers, to evaluate their association with observed clinical responses to LY3819253 and the disease state.

Samples may be used for research to develop methods, assays, prognostics and/or companion diagnostics related to the intervention target (S protein), the COVID-19 disease state, pathways associated with disease, and/or the mechanism of action of the study intervention.

Sample retention is described in Section 10.1.12.

8.9. Immunogenicity

Visits and times

At the visits and times specified in the SoA, venous blood samples will be collected to determine antibody production against LY3819253. The actual date and time (24-hour clock time) of each sample collection will be recorded.

Sample collection, handling, and use

Instructions for the collection and handling of blood samples will be provided by the sponsor.

Immunogenicity will be assessed by a validated assay designed to detect ADAs in the presence of LY3819253 at a laboratory approved by the sponsor. Antibodies may be further characterized for their ability to neutralize the activity of LY3819253.

Sample retention

Sample retention is described in Section 10.1.12.

8.10. Health Economics

This section is not applicable for this study.

9. Statistical Considerations

9.1. Statistical Hypotheses

This is an exploratory study with a primary objective of assessing safety and tolerability. Any hypothesis tests conducted for treatment comparisons will be exploratory in nature and conducted without adjustment for multiplicity.

9.2. Sample Size Determination

For Cohorts 1 - 3, approximately 24 participants will be randomized to receive one of three dose levels of LY3819253 or placebo. Additional participants may be required to ensure a minimum of 8 participants in each cohort complete 7 days of study assessments. Up to a maximum of 3 additional participants per cohort may be added.

Participant viral loads over time were simulated using a representative PK/PD model to enable a Monte Carlo assessment of the power of the trial to detect a 30% treatment difference in mean AUC (28 day) of viral load. This assessment revealed greater than 90% probability of meeting the following Bayesian critical success factor:

Pr ((mean AUC_{PL} – mean AUC_{LY})/ mean AUC_{PL} > 0.3) > 0.60 PL = placebo, LY = LY3819253

Additionally, the anticipated 6 participants per treatment provides greater than 80% probability (within each treatment arm) of observing safety events of reasonable prevalence (that is, at least 25%) to support the primary objective of safety assessment.

For the optional Cohort 4, up to 100 participants may be randomized in an approximate 1:1 ratio to receive either LY3819253 or placebo. The overall numbers of participants randomized to LY3819253 and placebo in this study will provide 60% power to detect a reduction in the rate of clinical worsening from 22% to 9% (one-sided alpha=0.05). Clinical worsening is defined as the proportion (percentage) of participants with any worsening on the NIAID ordinal scale from baseline to Day 15.

A participant is only allowed to receive one IV infusion in one cohort.

9.3. **Populations for Analyses**

This table defines the populations for analysis.

Population	Description
Entered	All participants who sign the informed consent form
Safety	All participants randomly assigned and who received study intervention.
	Participants will be analyzed according to the intervention they actually
	received.
Pharmacokinetic	All randomized participants who received study intervention and have
	evaluable PK sample. Participants will be analyzed according to the
	intervention they actually received.
Pharmacodynamic	All randomized participants who received study intervention and provided at
	least one post-baseline measure for the relevant endpoint. Participants will be
	analyzed according to the intervention they actually received.

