10.4.2 Pharmacodynamic Statistical Methodology

SARS-CoV-2 viral load

SARS-CoV-2 viral load will be measured using the cycle time (CT) from a polymerase chain reaction (PCR) assay. Higher CT values indicate a lower viral load.

SARS-CoV-2 viral load, including changes from baseline, will be summarized and plotted by treatment, and listed. Baseline is defined as the Day 1 predose assessment. Overlaying individual profiles of SARS-CoV-2 viral load data will also be presented graphically over time.

Changes from baseline in SARS-CoV-2 viral load data will be statistically analyzed using a mixed model for repeated measures (MMRM). The model will contain baseline as a covariate, treatment, day and treatment-by-day interaction as fixed effects, and subject as a random effect. The unstructured covariance matrix will be selected initially; if this analysis fails to converge another covariance structure will be selected based on AIC and BIC values. The least square (LS) means and treatment differences (LY3819253 minus pooled placebo at each dose level) will be calculated and presented with their corresponding 90% confidence intervals (CIs). All available data will be used in the analysis.

An example of the SAS code that will be used is as follows:

```
proc mixed data=xxx;
class trtmnt subject day;
model chg = base trtmnt day trtmnt*day / alpha=0.1 cl ddfm=kr2;
repeated day / subject=subject type=un;
lsmeans trtmnt*day / alpha=0.1 cl pdiff;
ods output lsmeans=lsm01 diffs=diff01;
run;
```

where chg is the change from baseline, base is the baseline in SARS-CoV-2 viral load data, day is the study day, and trtmnt is the treatment used in the comparison.

A Bayesian linear mixed effect model will be fitted to evaluate the critical success factor by Lilly statistics group with the model listed below:

 $y_{ijk} = \mu + \alpha \times base + \alpha_i + \beta_k + (\alpha\beta)_{ik} + \varepsilon_{ij} + \varepsilon_{ijk}$

Where y_{iik} : the change from baseline for treatment i, subject j at day k

μ: a constant common to all observations

 α : a fixed coefficient on the covariate baseline viral load

 $\alpha_{i:}$ a parameter corresponding to treatment i

 $\beta_{k:}$ a parameter corresponding to day k

 $(\alpha\beta)_{ik:}$ an interaction parameter corresponding to treatment i and day k

 ϵ_{ij} , ϵ_{ijk} : random error for between and within subject variability

prior μ , α , α_{i} , β_{k} , $(\alpha\beta)_{ik} \sim N(0, 100)$

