 $\varepsilon_{ij} \sim N(0, \sigma_1), \ \varepsilon_{ijk} \sim N(0, \sigma_2)$

 $\sigma_{1}, \sigma_{2} \sim uniform(0, 100) \text{ or } igamma(0.01, 0.01)$

the posterior of the following quantity will be assessed:

 $pr(\Delta_{anyLYdose} - \Delta_{placebo} < -0.3) > 0.6 \text{ at Day 7, 11, 15, and 22 in log base 10 scale.}$

SARS-CoV-2 viral load AUC

The AUC from Day 1 predose to Day 29 (AUC[0-D29]) will be calculated according to the linear trapezoidal rule using the measured SARS-CoV-2 viral load-time values above the lower limit of quantification. No imputations of missing data will be conducted. No AUC(0-D29) values will be calculated when Day 1 predose and/or Day 29 values are missing, or if there are more than 3 values missing in the profile.

The AUC(0-D29) will be summarized and plotted by treatment and listed.

Additionally, AUC(0-D29) data will be statistically analyzed using a linear model. The model will contain treatment as a fixed effect and baseline viral load as a covariate. The least square (LS) means and treatment differences (LY3819253 minus pooled placebo at each dose level) will be calculated and presented with their corresponding 90% confidence intervals (CIs). All available data will be used in the analysis.

An example of the SAS code that will be used is as follows:

```
proc mixed data=xxx;
class trtmnt;
model AUC = base trtmnt / alpha=0.1 cl ddfm=kr2;
lsmeans trtmnt / alpha=0.1 cl pdiff;
ods output lsmeans=lsm01;
ods output diffs=diff01;
run;
```

where AUC is the AUC(0-D29) data, trtmnt is the treatment used in the comparison, and base is the baseline viral load.

Similar Bayesian model listed in Section 10.4.2 by removing the day, interaction, and within subject error term will be applied for AUC measure analysis.

SARS-CoV-2 clearance

The proportion of patients that achieve SARS-CoV-2 clearance will be summarized by treatment in frequency tables, and listed.

In addition, the number of patients that achieve SARS-Cov-2 clearance will be analyzed using a Chi-square test to compare LY3819253 versus pooled placebo at each dose level, if there are sufficient data available.

An example of the SAS code that will be used is as follows:

```
proc freq data=xxx;
weight count;
table trtmnt*clear / chisq all;
run;
```

where trtmnt is the treatment used in the comparison, clear is the SAR-CoV-2 clearance (yes/no), and count is the corresponding number of patients.

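### The >90% in the sample size section is not power at a 30% reduction in viral load AUC: 30% is the criterion's own threshold, and a true 30% reduction would pass far less often

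*Protocol*

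**What the plan says.** Protocol 9.2 justifies the size of Cohorts 1-3 on viral load in two linked sentences. The first gives the purpose of the simulation, a "Monte Carlo assessment of the power of the trial to detect a 30% treatment difference in mean AUC (28 day) of viral load". The second gives the result: "This assessment revealed greater than 90% probability of meeting the following Bayesian critical success factor". The criterion follows directly: "Pr ((mean AUC_{PL} – mean AUC_{LY})/ mean AUC_{PL} > 0.3) > 0.60". SAP section 8 repeats the text.

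For the optional Cohort 4, the same section says that the study's overall numbers "will provide 60% power to detect a reduction in the rate of clinical worsening from 22% to 9" percent, with a one-sided alpha of 0.05.

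On the analysis side, SAP 10.4.2 says "A Bayesian linear mixed effect model will be fitted to evaluate the critical success factor by Lilly statistics group", and prints N(0, 100) priors for the change-from-baseline version of that model. For AUC it adds only this: "Similar Bayesian model listed in Section 10.4.2 by removing the day, interaction, and within subject error term will be applied for AUC measure analysis". The non-Bayesian AUC analysis is by dose: "treatment differences (LY3819253 minus pooled placebo at each dose level) will be calculated".

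**The concern.** Power to detect an effect ordinarily means the chance of success when that effect is the truth. The Cohort 4 sentence uses the phrase in that sense: 22% and 9% are the assumed true rates. A reader will carry the same meaning to the AUC sentence and conclude that a true 30% reduction would meet the criterion more than nine times in ten.

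The criterion cannot behave that way when 30% is also its threshold. If the truth sits exactly on the bar, the estimate falls above or below it about equally often, and the criterion further asks for 60% posterior probability of being above. A larger sample narrows the estimate around the bar without moving it to one side.

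What is at stake is interpretation. This is the only viral-load justification given for the size of Cohorts 1-3. Someone who takes the >90% at face value would read a failed criterion as good evidence against a 30% effect, although a true 30% effect would often fail.

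**Working it through.** **Inputs from the documents.** Threshold 0.3 and posterior cut-off 0.60 (Protocol 9.2, SAP 8); 6 active and 2 placebo participants per cohort (Protocol 4.1.1), so 6 per dose and 6 placebo when pooled over three cohorts; pooled placebo as comparator (SAP 10.4.2, non-Bayesian AUC model).

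**Assumptions of this check.** A near-flat prior. For the any-dose reading, the same true 30% reduction at all three doses.

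**The plan's figure.** The >90% cannot be rebuilt. The true AUC reduction generated by the PK/PD model, the variability and the simulation prior are not given, and neither is the meaning of LY in the criterion (each dose, any dose, or all doses pooled).

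**One comparison.** Let d = 0.7 × mean(PL) − mean(LY). With a positive placebo mean, a reduction above 30% is the same as d > 0. Under a near-flat prior the posterior of d is approximately normal around its estimate with standard error SE, so

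- pass when estimate / SE > z(0.60) = 0.253;
- at a true reduction of exactly 30%, d = 0 and estimate / SE is approximately standard normal;
- P(pass) = 1 − Φ(0.253) = 1 − 0.60 = **0.40**.

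Sample size and SD cancel. The result is the same for one dose (6 v 6) and for all doses pooled (18 v 6).

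**Any of three doses, shared placebo.** The three estimates are correlated because each uses 0.7 × mean(PL). P(at least one passes) = 1 − P(all three standardised estimates ≤ 0.253).

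- Equal SDs: correlation = 0.49 / (1 + 0.49) = 0.329, giving **0.697**.
- SD proportional to the mean: the active variance is also 0.49 times the placebo variance, so correlation = 0.49 / 0.98 = 0.5, giving **0.650**.

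**Any of three, independent comparisons.** 1 − 0.60³ = 1 − 0.216 = **0.784**. This is the most favourable of the arrangements considered.

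**More participants.** With up to 3 extra per cohort, the maximum is 24 + 9 = 33. An assumed split of 8 per dose and 9 placebo gives 0.658 to 0.704 for any of three with shared placebo, and leaves one dose at about 0.40.

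**Simulation check.** With 6 per dose and 6 placebo, t-based posteriors, normal and lognormal AUC and a range of assumed coefficients of variation, one dose passed 0.39-0.41 of the time and any of three 0.64-0.71, in line with the formulas.

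**What >90% requires.** For one dose the true d must exceed zero by 0.253 + 1.282 = 1.535 SE. For any of three with shared placebo the margin is about 0.63 SE (correlation 0.33) to 0.78 SE (correlation 0.5). Under a near-flat prior, then, the >90% needs a true reduction above 30%. How far above depends on variability that the documents do not give, so I put no percentage on it.

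**Other priors.** A zero-centred prior that is informative on the AUC scale pulls the estimate towards no effect and lowers the pass rates above. The N(0, 100) printed for the related model could act this way, depending on whether 100 is a variance or an SD and on the units of AUC, neither of which is stated. Only a prior favouring larger reductions would raise the figures.

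**The case against.** The best defence is that neither document says in one sentence that there is more than 90% power at a 30% effect. One sentence states an aim; the next reports the probability of meeting a criterion that is printed in full, so a careful reader can see what the >90% refers to. Part of this stands: the reported quantity is defined. But the second sentence presents the >90% as the outcome of the assessment that the first calls power to detect 30%, and the Cohort 4 sentence in the same section uses that phrase in its ordinary sense.

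A second defence is that the PK/PD model may predict a reduction well above 30%, in which case the >90% could be right. This stands in full. A reader might infer from the 40% that the simulation was miscalculated. The documents do not support that, because its inputs are not shown.

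A third is that 40% and 65-70% rest on an assumed flat prior, although SAP 10.4.2 prints one for the model it calls similar. This also stands as a limit on the exact figures. It does not rescue the literal reading, since a zero-centred prior moves the pass rate down.

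Finally, the study is exploratory (Protocol 9.1), its primary objective is safety, and no text ties a decision to the AUC criterion. That is correct and limits the consequence. A reader might also infer that Cohorts 1-3 are too small; nothing here shows that, because at a true 30% effect the pass rate for a single comparison does not depend on sample size.

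**Conclusion.** The concern holds as a fault in what the >90% is said to mean. Under a near-flat prior, a true 30% reduction meets the criterion about 40% of the time for one dose or pooled doses, and about 65-70% for any of three equally effective doses against shared pooled placebo. Independent comparisons would give at most about 78%, so the 65-70% should not be read as a ceiling. If some doses reduce AUC by less than 30%, the any-dose figure is lower. None of these readings reaches 90%.

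Put the other way, a true 30% effect would fail about 60% of the time for one dose or pooled, and about 30-35% for any of three with shared placebo. The 40% follows from the printed cut-off and the flat prior. The any-dose figures also need a reading of LY that the AUC criterion does not state.

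The damage is confined to how the viral-load justification for Cohorts 1-3 is understood. The separate safety rationale is untouched. The correction is worth making because the sentence attributes to the design a property it does not have.

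**What to change.** In both Protocol 9.2 and SAP 8, replace "power of the trial to detect a 30% treatment difference in mean AUC (28 day) of viral load" with wording such as: *probability of meeting the criterion for a reduction greater than 30%, assuming a true reduction of X% and variability Y*. Fill in X and Y from the PK/PD simulation. State the prior used for the AUC criterion, and say whether LY means each dose, any dose or all doses pooled. From the same simulation, report the success probability at true reductions of 30% and 0%, so that readers see both the chance of passing at the threshold and the chance of passing with no effect.

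The cost is a wording change in two places and two extra scenarios in an existing simulation. The downside is that the figure at 30% will look less favourable than the one now printed. No extra patients are needed.
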